Timing: Non-serious AE will be reported from the initial treatment with FCM through the completion of the study Day 35. Adverse events will be captured 28 days post the last dose of study drug for participants who receive study drug and terminate early from the trial. This can be completed via a phone call. All ongoing AE's related to FCM should be followed until they are no longer related, have taken a confounding medication or return to baseline grade.

Relationship (Causality): The Investigator will be asked to document his/her opinion of the relationship of the event to the study drug* as follows:

- **NONE** There is *no* evidence of any causal relationship
- **UNLIKELY** There is *little* evidence to suggest there is a causal relationship. There is *another reasonable explanation* for the

event (e.g., the participant's clinical condition, other concomitant treatments).

- **POSSIBLE** There is *some* evidence to suggest a causal relationship (i.e. there is a reasonable possibility that the adverse experience may have been caused by the agent). However, the influence of *other factors may have contributed* to the event (e.g., the participant's clinical condition, other concomitant events).
- **PROBABLE** There is *evidence* to suggest a causal relationship, and the influence of other factors is *unlikely*

*For the purpose of this trial, study drug is defined as FCM.

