2.3.4 Handling of Missing Data

A participant who withdraws from the study for any reason will be included in the analyses regardless of time on study. Methods for handling withdrawals and missing data will be specific to each endpoint to be analyzed. Missing data will not be imputed for descriptive statistical summaries in safety or efficacy.

For statistical inferential (paired t-tests) analyses, missing data will be imputed using last observation carried forward (LOCF) method for hemoglobin and other efficacy endpoints. e.g. for primary endpoint, hemoglobin, when Day 35 data is missing (subject has discontinued before Day 35, or measurement not taken at Day 35 though subject was not discontinued), Day 28 or last unscheduled result will be carried forward. If there is no post-baseline value observed, the worst value obtained from Day 35 of all subjects in the safety population will be used. The worst value is defined as the lowest value for hemoglobin, ferritin, TSAT and reticulocyte hemoglobin content.

Dates missing the day or both day and month of the year will adhere to the following conventions to classify TEAE and to classify prior/concomitant medications.

- A medication with a completely missing start date will be considered a prior medication. A medication with a completely missing stop date will be considered a concomitant medication.
- If complete AE onset date is missing and AE end date is on or after the first dose date then it will be counted as a treatment emergent AE (TEAE) for the study. If complete AE onset date is missing and AE end date is before the first dose date then it will not be counted as a TEAE for the study.
- If an AE or a medication has a partial missing start or stop date, the following rules will be used for imputation:
 - If year is present but month and day are missing, impute start date as January 1 of that year or first dose date if the year is the same as the year of first dose date and impute stop date as December 31 of that year.
 - If year and day are present but month is missing, impute start month as January or the month of the first dose date if the year is the same as the year of first dose date and impute stop month as December.
 - If year and month are present but day is missing, impute start date as first day of that month or first dose date if the year and month are the same as the year and month of first dose date and impute stop date as last day of that month.

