7.1 ADVERSE EVENTS

Adverse events (AEs) will be coded by System Organ Class (SOC) and Preferred Term (PT) using the Medical Dictionary for Regulatory Activities (MedDRA) dictionary. Adverse event

summaries will exclude preferred terms that describe asymptomatic serum ferritin, TSAT, and reticulocyte values (or changes). This approach is justified by the reporting of these values in efficacy summaries and is consistent with the protocol-defined reporting standards for hemoglobin/hematocrit and low iron indices. For the purposes of this study, non-serious anemia (hemoglobin or hematocrit below the normal range or worsened from baseline) or iron deficiency (iron indices below the normal range or worsened from baseline) will not be considered adverse events. Anemia or iron deficiency will be considered end points if an intervention is required.

A treatment-emergent adverse event (TEAE) is defined as an event with onset date on or after the study drug start date. Partial date TEAE classification rules refer to Section 2.3.4. Only TEAEs will be included in summary tables.

The incidence of TEAEs will be summarized as the number (percentage) of subjects with TEAEs within SOC and PT. Subjects who report the same PT on multiple occasions will be counted once for the PT: under the highest severity (severe > moderate > mild) CTCAE when summarized by severity and under the closest relationship (probably related > possibly related > unlikely related > none) to study drug when summarized by relationship. If a subject reports multiple PT for a SOC, the subject will be counted only once for that SOC. Events with unknown severity or relationship will be counted as unknown.

TEAEs will be summarized as below.

- An overview table, including number of subjects with
 - TEAEs
 - serious TEAEs
 - study drug related TEAEs
 - study drug related Serious TEAEs
 - TEAEs by severity
 - TEAEs leading to study drug discontinuation or withdrawal from study
 - TEAEs leading to death
- TEAE by SOC
- TEAE by PT
- TEAE by SOC and PT
- TEAE by SOC, PT, and Severity (CTCAE)
- Study drug related TEAEs by SOC, PT
- Serious TEAEs by SOC and PT
- Study drug related serious TEAEs by SOC and PT

- TEAEs leading to study drug discontinuation or withdrawal from study by SOC and PT
- TEAEs leading to death by SOP and PT

Unless otherwise stated, all TEAE tables will be sorted by SOC and PT in decreasing frequency of the number and percentage of subjects.

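### The SAP's missing-month rule for AE onset has no floor at the first dose date, so a post-dose AE can be dated before dosing and left out of every AE summary table

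*SAP*

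**What the plan says.** SAP 2.3.4 (Handling of Missing Data) has three rules for partly missing start dates of AEs and medications.

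- Month and day missing: use "first dose date if the year is the same as the year of first dose date and impute stop date as December 31" for the stop. In the first-dose year, the start becomes the first dose date.
- Day missing: use "first dose date if the year and month are the same as the year and month of first dose date". Again the fallback is the first dose date.
- Month missing: "If year and day are present but month is missing, impute start month as January or the month of the first dose date", the second option applying "if the year is the same as the year of first dose date and impute stop month as December". Here only the month is borrowed from the first dose, and the recorded day stays.

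A separate rule uses the end date: "If complete AE onset date is missing and AE end date is on or after the first dose date then it will be counted" as treatment-emergent. It covers only onset dates that are missing altogether.

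SAP 7.1 attaches the consequence. "A treatment-emergent adverse event (TEAE) is defined as an event with onset date on or after the study drug start date", partial dates are referred back to 2.3.4, and "Only TEAEs will be included in summary tables". SAP 2.3.2 applies the same conventions to Study Day and durations.

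Protocol 7.1 sets the collection window: "Non-serious AE will be reported from the initial treatment with FCM through the completion of the study Day 35". Protocol 7.3 starts SAE reporting on the day of initial treatment.

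**The concern.** The protocol collects AEs only from first dose, so an AE in the database should have its onset on or after that date. The missing-month rule can assign a date that the collection rule excludes, and the TEAE definition then treats the AE as pre-treatment. Where the protocol's window is followed, an error of this kind can only lower AE counts.

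The ordering is also odd. An AE with no onset information but a post-dose end date counts as a TEAE, while the same AE with its day and year known can be dropped.

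Safety is part of the primary objective of this single-arm study. One participant lost from a table row is 1/36 = 2.8 percentage points of incidence if 36 are treated.

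**Working it through.** The plan states no figure on this point, so there is none to reproduce. The check applies the rule literally.

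**Inputs**
- Rule (SAP 2.3.4): keep the recorded day and year; month = month of first dose if the years match, otherwise January.
- TEAE (SAP 7.1): onset date on or after the study drug start date.
- Follow-up (Protocol 6.3.5): Day 35 ± 1 day, with the first dose on Day 0.
- Study Day (SAP 2.3.2): the first dose date is Study Day 1, and the day before it is Study Day −1.

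**Worked example.** First dose 20 March 2020, so Day 35 is 24 April. True onset 5 April, recorded as day 05, month unknown, 2020.
- The collection window runs from 20 March to 24 April and contains only one fifth of a month, 5 April: 16 days after dosing, Study Day 17.
- The rule gives 5 March 2020. Study Day = 5 March − 20 March = −15. Not a TEAE.
- The end-date rule does not help, because the onset is only partly missing.

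For this dose date, every onset from 1 to 19 April (Days 12 to 30) is moved before dosing, which is 19 of the 36 possible onset days. An onset on 20 April is imputed to 20 March and counts.

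**When it fails.** The onset falls in a later month of the first-dose year, on a day of the month earlier than the first-dose day.

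**Enumeration.** Every first-dose date in a calendar year was crossed with every onset day. Share = (imputed onsets before first dose) / (dose dates × onset days).

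| Onset days | 2020 (366 dose dates) | 2021 (365 dose dates) |
|---|---|---|
| 0 to 35 | 5,066 / 13,176 = 38.4% | 5,043 / 13,140 = 38.4% |
| 0 to 34 | 5,020 / 12,810 = 39.2% | 4,996 / 12,775 = 39.1% |
| 0 to 36 | 5,122 / 13,542 = 37.8% | 5,100 / 13,505 = 37.8% |
| 0 to 14 | 1,155 / 5,490 = 21.0% | 1,155 / 5,475 = 21.1% |

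Over Days 0 to 35, the two neighbouring rules give 0 pre-dose onsets, and so do onsets in the next calendar year (the January option). In a further 31 (2020) or 38 (2021) combinations the imputed date does not exist, such as 31 April, and the SAP does not say what to do.

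**After the fix.** Taking the later of the imputed date and the first dose date gives 0 pre-dose onsets over all valid imputed dates (2020, Days 0 to 35). In the example, the onset becomes 20 March, Study Day 1, and the AE is a TEAE.

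**The case against.** The strongest reply is that the rule will hardly ever be used. It needs a record with day and year known but month unknown. AEs are assessed at Days 0, 7, 14, 28 and 35 (Protocol Table 1), the investigator records the date and time of onset (Protocol 7.2) and must verify the eCRF (Protocol 9.8.1), and there are at most about 36 participants. The number of affected AEs may well be zero. This stands, and it is why the point is minor. It does not make the rule right.

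The sentence introducing the partial-date rules mentions dates missing the day, or both day and month, but not the month alone. One could argue that the rule is merely loose drafting. But the bullet names the missing-month case explicitly, so a programmer would apply it.

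A reader might infer that the AE vanishes from the report. The documents do not support that. The exclusion covers the AE summary tables, including the serious, related and special-interest ones. SAP 2.1 provides for the ICH-required listings, the laboratory and vital-sign tables do not depend on TEAE status, and SAEs are reported to the sponsor within 24 hours (Protocol 7.3).

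A reader might also infer that any imputed onset before first dose should be moved to first dose. That goes too far. An ongoing AE recorded as February 2020, day missing, with a first dose on 20 March 2020, is imputed to 1 February. A general floor would override the recorded month and turn it into a TEAE. The floor belongs only where the pre-dose date is created by borrowing the month.

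**Conclusion.** The rule is wrong as written, with a small expected effect. It can date a post-dose AE before dosing, against the protocol's own collection window, and no other rule in the SAP corrects this.

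The 38% (range 37.8% to 39.2% over the Day 35 ± 1 window) and the 21% assume evenly spread dose and onset dates. They apply only to AEs with day and year known and month missing, in which group they measure how often the rule fails. They are not shares of all AEs. The documents do not say how many such records to expect, so no overall loss can be computed.

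This is worth correcting before database lock because it is cheap, and not because it is likely to change the safety conclusions.

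**What to change.** Amend only the missing-month bullet in SAP 2.3.4, and only for AE onset. Suggested text:

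> For an AE start date with day and year known, month missing, and the year equal to the first-dose year, use the month of first dose. If the date so formed precedes the first dose date, and the AE end date is not before the first dose date, set the onset to the first dose date and classify the AE as treatment-emergent.

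The SAP should say that a missing end date counts as not before first dose. Medication start dates in the same bullet should be left alone, since a medication can properly start before dosing. A short clause on imputed dates that do not exist would close the other gap.

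The cost is one or two sentences, with no effect on the efficacy analyses. There is a small downside: the imputed onset may be earlier than the true one (in the example, Study Day 1 instead of 17). That affects Study Day, duration and, for events of special interest, the time to onset planned in Protocol 8.5.3. It does not affect the TEAE count.

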2.4 POOLING OF CENTERS

The study centers are not planned to be used as a stratification factor nor a covariate in the statistical modeling and testing, therefore it is not necessary to pool small centers together.

2.5 ANALYSIS SOFTWARE

All summaries and statistical analyses will be generated using SAS® version 9.4 or higher.

3. STUDY SUBJECTS

3.1 DISPOSITION OF SUBJECTS

Disposition will be summarized for all screened subjects and the number of subjects in Safety Population will be summarized in each investigative site.

The disposition will include the following:

- Participants who are screened
- Participants who are included in Safety Population
- Participants who complete the study
- Participants who discontinue the study

The number and percent of subjects will be summarized for each reason for premature discontinuation.

3.2 PROTOCOL DEVIATIONS

The clinical team will identify deviations and the deviations will be identified in the database. The number and percent of participants with clinically important protocol deviations will be summarized for each type of deviation based on the safety population.

4. DEMOGRAPHY AND BASELINE CHARACTERISTICS

4.1 DEMOGRAPHY AND BASELINE CHARACTERISTICS

Demography data such as sex, age, age group (1 to <12 and \geq 12 to 18 years), race, ethnicity, body height, body weight, BMI and BMI group (underweight \leq 18.5, 18.5 < normal weight \leq 24.9, 25 < overweight \leq 29.9, obesity = BMI of 30 or greater) will be summarized with descriptive statistics or frequency counts for all patients in the safety populations.

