Multiple parenteral iron products are available. These products vary in the way that iron is complexed, which influences the total amount of iron that may be administered during a single administration. Numerous other differences differentiate the products. However, all appear to effectively release iron post administration and can restore iron deficit in the patient. Previous studies with parenteral iron sucrose (Venofer®) have been performed in the pediatric population [Michaud, 2002; Pinsky, 2008; Surico, 2002]. Iron doses have varied in these studies, and the data demonstrates the efficacy and safety of Venofer® in doses up to 7 mg iron/kg (or 200 mg) administered over 3 minutes, which was shown to be beneficial to both the child and health care facility [Michaud, 2002].

Ferric Carboxymaltose has been characterized as an iron complex (Type 1) with a molecular mass of about 150,000 Daltons. The solution is a dark brown color with a near

neutral pH (5.0 to 7.0) and a physiological osmolarity permitting administration of higher single doses in short time periods. Although no randomized interventional studies have been completed with FCM in the pediatric population to date, the product has been used successfully to address iron deficiency in pediatric patients with ulcerative colitis and Crohn's disease. A non-interventional, retrospective observational data collection reported FCM exposure in 79 patients aged 2 to 18 years with a mean age of 12.7 years. In these patients, FCM was found to be safe, well-tolerated, and effective in increasing Hgb, ferritin, and TSAT [Favreau, 2017].

The proposed study will provide safety and efficacy data on the use of FCM in pediatric patients (aged between 1 and 18 years) with IDA. FCM will be administered in 2 doses at 15 mg/kg maximum single dose of 750 mg with a total maximum cumulative dose of 1500 mg. The ability to infuse higher doses of elemental iron should permit repletion in fewer overall infusions, and in doing so may ultimately permit fewer visits to the treating facilities.

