6. STUDY PROCEDURES

6.1. Informed Consent

Prior to any study specific procedures, the investigator must explain to each participant the nature of the study, its purpose, procedures to be performed, expected duration, and the benefits and risks of study participation. After this explanation, the participant (who for this trial is 1 -18 years old) must assent, if appropriate, and his/her legal guardian (who is above age of legal consent) voluntarily sign an informed consent statement (Required Elements of Informed Consent, 21 CFR 50.25). The Code of Federal Regulations (CFR) is a codification of rules and regulations of the US government. Subjects who are too young to sign an informed consent form, but mature enough to understand the study, will provide informed assent per local law. The subject must be able to understand that he or she can withdraw from the trial at any time and for any reason. The participant's legal guardian will be given a copy of the signed consent form.

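### SAP 4.1 groups BMI with one fixed set of cut-offs for ages 1 to 18, so the baseline table may label many young children underweight by artefact; two small interval gaps also need closing.

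*SAP*

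**What the plan says.** SAP 4.1 lists BMI and BMI group among the baseline items to be tabulated for the safety population. The group boundaries read "18.5, 18.5 < normal weight", then "24.9, 25 < overweight", and the last group is "obesity = BMI of 30 or greater". Written as intervals, underweight is BMI ≤ 18.5, normal is > 18.5 to ≤ 24.9, overweight is > 25 to ≤ 29.9, and obesity is ≥ 30.

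The same sentence defines an age split, beginning "age group (1 to <12 and", but does not tie the BMI limits to it or to sex. Protocol 1.1 describes the population as "pediatric patients (aged between 1 and 18 years) with IDA", and Protocol 6.1 gives the same age range.

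No other part of the SAP modifies the BMI groups. SAP 2.1.1 sets one decimal for weight and height summary statistics but gives no rule for rounding BMI before grouping.

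**The concern.** BMI changes with age during childhood, so a single limit cannot mean underweight, or obese, both in a toddler and in a 17-year-old. The SAP recognises this kind of age dependence elsewhere. Appendix 1.2 bands heart rate and blood pressure by age, and Appendix 1.1 varies several laboratory limits and the hemoglobin grades by age and, in part, by sex. BMI is treated differently, and no reason is given.

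What is at stake is the description of the study population. Protocol 1.1 names poor weight gain among the consequences of iron deficiency in children. A reader who sees a large underweight fraction could take it for a feature of the disease when it partly reflects the cut-off.

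Separately, the four intervals do not meet at two of the three boundaries. A participant with a known BMI could have no group, and the counts would then not add up to the population total.

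**Working it through.** The plan states no BMI figure, so there is none to reproduce. The check has three parts.

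**1. What the rule means in kilograms.** The inputs are the limits 18.5 and 30 from SAP 4.1. Weight at a limit = limit × height² (height in metres).

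- Underweight limit at 0.90 m: 18.5 × 0.81 = 15.0 kg
- At 1.10 m: 18.5 × 1.21 = 22.4 kg
- At 1.30 m: 18.5 × 1.69 = 31.3 kg
- Obesity limit at 1.10 m: 30 × 1.21 = 36.3 kg

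As an illustration with an assumed body size, 18 kg at 110 cm gives 18 / 1.21 = 14.9, which the rule calls underweight. These figures restate the rule; they do not show how many children fall below the limit.

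**2. How many young children could carry the label.** The documents give no BMI mean or SD, so both are assumed. With a normal distribution of mean m and SD s, the share is Φ((18.5 − m)/s). For example, m = 16 and s = 2 give Φ(1.25) = 0.894.

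| Assumed mean BMI | Share labelled underweight, SD 1.5 to 3 |
|---|---|
| 15 | 88% to 99% |
| 16 | 80% to 95% |
| 17 | 69% to 84% |
| 18 | 57% to 63% |
| 19 | 37% to 43% |

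The share passes one half exactly when the median BMI of these children is below 18.5.

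**3. The gaps.** The four intervals were applied literally to every BMI from 10.0 to 45.0.

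- At two decimals, 24.91 to 25.00 (10 values) and 29.91 to 29.99 (9 values) have no group, 19 values in all. No value falls in two groups.
- If BMI is first rounded to one decimal, only 25.0 has no group.
- Example: 64.0 kg at 160.0 cm gives 64.0 / 2.56 = 25.0, which is unclassified either way.

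The expected number unclassified is n × P(BMI in a gap). Here n = 36, the approximate maximum in SAP 1.3.3, and the means and SDs are again assumed.

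| Mean, SD | Expected (chance of at least one), unrounded | Same, rounded to one decimal |
|---|---|---|
| 16, 2 | about 0 | about 0 |
| 20, 4 | 0.18 (17%) | 0.16 (15%) |
| 24, 5 | 0.42 (35%) | 0.28 (25%) |
| 25, 4 | 0.53 (41%) | 0.36 (30%) |

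The expected number is below one in every scenario tried.

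**The case against.** The strongest reply is that very little depends on this item. BMI group is a frequency count in a baseline table. The paired t-tests in SAP 6.1 and 6.2 do not use it, and no BMI subgroup, covariate or safety rule is planned. Continuous BMI, height, weight, age and age group are summarized alongside it, so a reader is not dependent on the label. All of this stands, and it is why the point is minor.

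A reader might infer that the table will label most young children underweight, or that the whole cohort will look underweight. The documents support neither. The first needs a median BMI below 18.5 in the young children, which is an assumption. The second also needs the age mix of this trial, which is not given; the mean age of 12.7 years in Protocol 1.1 belongs to a separate retrospective group.

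A reader might also infer that some participants will go unclassified. The gaps make that possible, but with at most about 36 participants the expected number is below one. SAP 2.1 allows a separate category for unknown or missing data, which could make an unplaced child visible, although a BMI of 25.0 is neither unknown nor missing.

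Finally, calling the limits adult cut-offs goes beyond the text, which shows only that they do not depend on age or sex.

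None of this supplies a reason for one fixed set of limits from age 1 to 18, or closes the gaps.

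**Conclusion.** The point holds as a minor one. It is a stated rule, not an omitted detail, and it may put misleading labels on many young children in a reported table. The size depends on an assumed BMI distribution: 57% to 99% of young children labelled underweight for a mean of 15 to 18, and 37% to 43% for a mean of 19, with SDs of 1.5 to 3 and normality assumed throughout. The weight limits and the two gaps follow directly from SAP 4.1 and need no assumption about body size. The gaps are a drafting slip with little expected effect. No primary, secondary or safety conclusion changes.

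**What to change.** In SAP 4.1, replace the fixed groups with age- and sex-specific BMI-for-age percentile or z-score categories taken from one named growth reference. State a rule for children under 2 years that uses the height and weight actually collected; the schedule lists only height, and whether recumbent length is recorded cannot be seen. Define the categories as contiguous intervals so that every value has exactly one group. Keep the summary of continuous BMI.

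No new data collection should be needed, because height and weight are in the schedule of activities and age and sex are in the same baseline table. The cost is choosing and justifying one reference for a multi-national study, plus a little programming. If the sponsor prefers to keep fixed groups, making the intervals contiguous (normal > 18.5 to < 25, overweight 25 to < 30, obesity ≥ 30) removes the unclassified values but leaves the age problem in place.
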